ICR will exclude pregnant and breastfeeding women from this study due to ethical concerns. We will also exclude children under the age of 18 for the same reason. Non-English speaking individuals will be excluded to ensure that comprehension and understanding of the ICD and test parameters is without question. Full time employees of either ICR, Inc. or the sponsor will be excluded to ensure that coercion is not an issue. Individuals sensitive to either mosquito bites, insect repellents, or skin care skin products will be excluded to avoid placing them at risk. Although the groups of people that ICR would exclude from using as test subjects would certainly represent individuals that could use repellents, we feel justified for not including them for the reasons that are mentioned above.

ICR will only include individuals attesting to be healthy in this study who are available to travel to distant field locations. These subjects need to be capable of reading and understanding English.

The database of potential test subjects that we select our subjects from, is as representative of potential repellent users as we are able make it in terms of both practical and ethical considerations. Our test subjects need to be in good health to withstand the rigors of field testing. They must be available to travel to out of state test locations. Test subjects must be able to speak and understand English in order to truly be informed and comprehend the scope of the study as explained to them. We will accept individuals between the ages of 18 to 65. This age group represents a large portion of the population who through their diverse activities would both encounter mosquitoes and could have a need to use insect repellents.

Page 10 of 31

Protocol No.: G0590307001A044 ICR Project No.: 0307-059-0155

ICR will select individuals from our database of potential test subjects. This will be accomplished by drawing numbers that correspond to a particular test subject. We will attempt to select even numbers of male and female test subject to eliminate any gender bias to attractiveness to mosquitoes.

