It is recognized that mosquitoes are vectors of many diseases and this issue is clearly communicated to potential test subjects. Since the EPA requires demonstration of the repellency of mosquitoes known to carry specific diseases such as the WNV in order to substantiate related product claims, the sponsor is compelled to conduct field testing in areas in which test subjects will attract these potential vector species. While the potential for contracting disease cannot be fully eliminated, that risk is reduced by avoiding conduct of the study in an area known to be associated with current incidents of mosquito and other insect-borne disease. Appropriate mosquito abatement authorities in the region of the proposed test site will be consulted immediately prior to the initiation of the field study to confirm that there has been no recent outbreak of mosquito or other insect-borne disease in that area.

The CDC estimates that only about 1 in 5 people who contract WNV will be affected. About one in 150 people infected with WNV will develop severe illness and about 4 of 5 will show no symptoms. Most people who have developed serious symptoms have been the elderly or those with a compromised immune system. The principal carriers of the WNV belong to the Culex genus (a genus is a group of similar species). This particular genus of mosquitoes is not common in areas where we will be conducting the study. While the risk of contracting WNV is considered to be low, no guarantees can be offered.

Georgia reported 8 cases of West Nile Virus, one case of Eastern Equine Encephalitis, one case of La Crosse Encephalitis in 2006. The La Crosse Encephalitis affects predominantly children under the age of 16.

Of the 8 cases reported in Georgia, one incidence of the West Nile Virus was reported for Chatham County, the proposed Georgia site of the study.

Florida reported 3 cases of West Nile Virus, one case of Eastern Equine Encephalitis and no other arbovirus type cases in 2006. None of these cases occurred in Lee County, Florida, the proposed study site.

Both the Mosquito Abatement Districts in Chatham County, Georgia, and in Lee County, Florida, monitor for disease bearing mosquitoes on a weekly basis and have agreed to supply ICR with that data for one week before and one week during the test. The study will be conducted only if surveys prior to the test are negative.

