## DISCOMFORT AND HAZARD

Mosquitoes are the primary vectors (carriers) of many diseases. Fortunately, most of these diseases do not occur naturally in the United States. Diseases like malaria and dengue are occasionally introduced by travelers, for example, two cases of naturally acquired malaria have been diagnosed in northern Virginia. Mosquitoes are also known to carry various types of encephalitis viruses. Currently the West Nile Virus (WNV) is widespread throughout the U.S. This mosquito-borne virus has caused much concern in some areas. The state of Georgia had 8 reported cases of WNV in humans in 2006, while Florida had 3 cases of WNV in humans in 2006. The principal carriers of the WNV belong to the Culex genus (a genus is a group of similar species). These mosquitoes are not common along the coast of Georgia or Florida in the areas where we will be conducting the study. The percentage of mosquitoes carrying WNV is small. Of those people bitten by an infected mosquito only a small percentage will contract WNV. Only a few of those people developing symptoms of WNV, will

Page 15 of 31

Mosquito Repellent Field Test, Florida & Georgia

Protocol No.: G0590307001A044 ICR Project No.: 0307-059-0155

develop serious symptoms. Most people who have developed serious symptoms have been the elderly or those with a compromised immune system. The most common symptoms of WNV are mild illness with fever, headache, and body aches. While the risk of contracting WNV is considered to be low, no guarantees can be offered. After the study completion, any subjects experiencing any of the above symptoms should seek medical attention. In the event that a study related injury or illness should occur, test subjects would be instructed to seek medical attention through a health care provider, at ICR's expense. Test subjects would be instructed to submit study related bills to ICR. ICR will incur the cost of any study related bills.

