#### Test Subject Recruitment

ICR has been conducting repellent studies for over twenty years. During this time ICR has amassed a large list of potential study subjects. These subjects also refer friends and colleagues to us. When a repellent study date has been established, ICR will contact potential study subjects by telephone and

Page 17 of 31

<sup>2 L.C. Rutledge and R. K. Gupta, 1999, Variation in The Protection Periods of Repellents on Individual Human Subjects: An Analytical Review, Journal of the American Mosquito Control Association, 15(3):348-355

Protocol No.: G0590307001A044 ICR Project No.: 0307-059-0155

briefly discuss the study, the date of the study, and location. Any study specific inclusion/exclusion requirements will also be mentioned at this time. When the number of interested subjects required for a particular study has been met, ICR will stop recruitment.

ICR uses the following initial telephone script to recruit test subjects:

"ICR will be conducting a repellent project on these dates, (Month, Day(s), Year), at (exact study site) would you be available to participate in this study?"

If the potential test subject is available, the inclusion/exclusion criteria will be discussed in detail and verified whether the subject qualifies to participate. The ICD will also be discussed with the test subject at this time. In addition, ICR will mail a copy of the ICD to each interested test subject for their review. They will be instructed to contact the P.I. to verify receipt of the ICD and to ask any ICD or study related questions they may have.

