#### Treatment Groups

There will be two groups for each test location(Georgia and Florida): a treated group of twelve subjects whose arms will be treated, and an untreated (control) group of two test subjects whose arms will be untreated. Subjects will be given a subject number. They will be assigned to the groups by lottery selection of the subject number.

Page 19 of 31

Protocol No.: G0590307001A044 ICR Project No.: 0307-059-0155

Personnel preparation

All test subjects will complete and will sign an "Informed Consent Document" prior to acceptance as a test participant.

On the evening prior to the first day of testing, the outside of the shoes of each test subject, the controls and the ICR staff will be treated with a 0.5% permethrin aerosol to help prevent ticks from crawling on test participants in the test areas. This treatment will not affect the test but will help protect the people involved from ticks. Permethrin has a low vapor pressure and will not interfere with the repellency of the treated arms.

Females will be required to perform an over the counter pregnancy test that will be supplied by ICR. They will do this the morning of the test. The results will be verified by a qualified female ICR staff member. They may not participate if they are pregnant or breastfeeding. The results of this pregnancy test will be kept confidential and will not be disclosed to anyone other than the test subject and the P.I..

The evening before the study is scheduled to begin, the test subject's arms will be measured in the following manner for demarcation of the 250 cm^2 test area:

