## Criteria for Test Cancellation

The study could be cancelled for several reasons; the first would be inclement weather. If weather conditions on site present unsafe circumstances for test personnel the study will be cancelled. These conditions include severe storm threats, high wind, or threat of lightning.

Additional reasons for test cancellation would be insufficient target insect activity. Any health concerns, the presence of WNV, or test material related reactions could also be reason for cancellation.

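### The protocol names a compromised immune system as a risk factor for serious West Nile illness, but no eligibility criterion names immune status and the general health attestation may miss it.

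*Protocol*

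**What the plan says.** Under RISK CHARACTERIZATION AND MINIMIZATION (risk 3), and again under DISCOMFORT AND HAZARD, the Protocol describes who becomes seriously ill with West Nile virus: "Most people who have developed serious symptoms have been the elderly or those with a compromised immune system". Both sections call the risk low but decline to guarantee against it.

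Eligibility is set out in several places:

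- SUBJECTS gives the age range, "We will accept individuals between the ages of 18 to 65", and a general health rule, "ICR will only include individuals attesting to be healthy in this study". It links the need for good health to coping with field work.
- TEST SUBJECTS lists sex, age, race and literacy. Its ineligibility list covers pregnancy and breastfeeding, full-time employment at the testing laboratory, sensitivity to bites or products, attractiveness to mosquitoes, smoking and alcohol, cosmetics, and clothing.
- STUDY RATIONALE and risks 1 and 2 add only a history of reactions or allergy.
- Test Subject Recruitment says that on the telephone "the inclusion/exclusion criteria will be discussed in detail and verified whether the subject qualifies to participate".

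Site-level safeguards are also stated. Among them are "The study will be conducted only if surveys prior to the test are negative" and, under Criteria for Test Cancellation, "Any health concerns, the presence of WNV, or test material related reactions could also be reason for cancellation".

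**The concern.** The protocol identifies two groups who fare worst from an infection that the study could transmit, then writes a criterion for only one of them. The age cap deals with the elderly. Nothing specific deals with people whose immune system is compromised.

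The endpoint makes this relevant. A scored bite on a treated arm is a completed blood meal (STUDY RATIONALE; Criteria for Test End Point), so the design accepts some feeding by wild mosquitoes. If an infected mosquito fed on an immunocompromised volunteer, the protocol's own account says that person would be among those most likely to become seriously ill. Only subject safety is at stake. The estimate of protection time does not depend on it.

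**Working it through.** No sample-size, power or event figure is involved, so the check sets each subject-level risk in the Protocol beside the criterion that answers it.

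| Risk named | Where named | Matching criterion |
|---|---|---|
| Pregnancy, breastfeeding | SUBJECTS | Named in the ineligibility list; pregnancy also tested on the study day |
| Reaction to mosquito bites | Risk 2 | Named in the ineligibility list |
| Reaction to repellents or skin care products | Risk 1 | Named in the ineligibility list |
| Serious West Nile illness: older age | Risk 3; DISCOMFORT AND HAZARD | Age 18 to 65, in SUBJECTS and TEST SUBJECTS |
| Serious West Nile illness: compromised immune system | Risk 3; DISCOMFORT AND HAZARD | None names it; only the general health attestation in SUBJECTS |

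The immune factor is mentioned twice as a risk and not once as a criterion. Protocol Amendments 1 to 10 do not add it.

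**Does the health attestation close the gap?** Three features make that uncertain. Health is not defined. The reason given for requiring it is fitness for field work, not susceptibility to infection. And it is absent from the lists under TEST SUBJECTS, so a screener working from those lists would not meet it.

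**Who is affected.** Each location has "a treated group of twelve subjects whose arms will be treated, and an untreated (control) group of two test subjects", which is 12 + 2 = 14. Over two locations that is 14 × 2 = 28, the total given in SUBJECTS. All 28 count, for two reasons. Screening comes before the lottery that assigns treated and control roles, so nobody is known to be a control when the question would be asked. And controls bare untreated skin: under NEGATIVE CONTROL, mosquitoes are brushed off after counting in order to keep bites few, which does not guarantee none.

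**Exposure.** Breakdown of a treated arm needs two blood-feeding bites, so a subject whose two arms both break down has had at least 2 × 2 = 4. Isolated bites restart the count, so this is a floor. It applies only if breakdown occurs; an arm may reach 12 hours without it.

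**What cannot be computed.** The documents give no prevalence of immune compromise among volunteers, no infection rate per bite, and no rate at which the attestation would miss someone. No probability follows.

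**The case against.** The strongest reply has five parts.

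1. **Nothing is contradicted.** The risk sections describe who becomes seriously ill; they never promise to screen those people out. That is correct. A reader might infer that the protocol breaks its own rule, but it does not. The point is that a foreseeable risk group is left to a general rule.

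2. **The health rule is binding.** SUBJECTS carries operative criteria that appear nowhere else, such as the exclusion of sponsor employees, and the criteria are gone through before consent. This stands. It would be wrong to infer that the protocol has no health criterion. What remains is that an undefined self-attestation may not be read as covering someone who feels well on treatment.

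3. **The consent form may already ask.** The ethics board's comments show that it contains a numbered suitability checklist, whose items are largely not shown. A reader might infer that volunteers are never asked about immune status; the documents do not support that. If the checklist asks, the safety gain falls to making the two documents agree.

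4. **Risk is already low and disclosed.** Surveys must be negative, the main carrier genus is uncommon at the sites, and "The percentage of mosquitoes carrying WNV is small". Exposures last 5 minutes, volunteers are told of the disease risk and may withdraw, and the protocol likens the risk to that of ordinary outdoor activity. All of this lowers the chance of infection for everyone, and disclosure allows self-exclusion. None of it screens for the group likely to fare worst. The Georgia county had one reported West Nile case in 2006, and cancellation for the virus is discretionary.

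5. **The ethics board raised no such gap.** The comments shown are detailed and do not mention immune status. That is modest evidence, not an answer.

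**Conclusion.** The point holds as a low-absolute-risk safety improvement with medium confidence. The protocol twice names immune compromise as a risk factor, its stated criteria never name it, and the one general rule that might cover it is undefined and sits outside the formal lists. It concerns all 28 recruits.

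Its size cannot be put as a probability. A reader may be tempted to assume a prevalence and calculate the chance of enrolling at least one such person. The documents offer no anchor for that input, and the calculation would presuppose the very screening failure in question. Nor does the point show that anyone would be harmed, or bear on the validity of the protection-time results.

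The conclusion rests on one judgement, that a person could honestly attest to being healthy while immunocompromised, and on one unknown, the content of the consent checklist.

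**What to change.** - **Ineligibility list under TEST SUBJECTS:** add a line such as *Test subjects must not have a known immune-system disorder and must not currently be taking immune-suppressing treatment (for example chemotherapy, transplant medication or systemic corticosteroids).*
- **Eligibility requirements under TEST SUBJECTS:** repeat the health attestation now found only in SUBJECTS.
- **Test Subject Recruitment:** ask both when the criteria are discussed by telephone.
- **Consent form:** if the suitability checklist already asks about immune status, carry that item into the ineligibility list so that the two agree; if not, add a matching line.

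The cost is one protocol amendment needing ethics board approval, a limited medical disclosure by each volunteer to the screener, and occasional replacement of a volunteer from the laboratory's database. No procedure is added and the analysis does not change.

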## DISCOMFORT AND HAZARD

Mosquitoes are the primary vectors (carriers) of many diseases. Fortunately, most of these diseases do not occur naturally in the United States. Diseases like malaria and dengue are occasionally introduced by travelers, for example, two cases of naturally acquired malaria have been diagnosed in northern Virginia. Mosquitoes are also known to carry various types of encephalitis viruses. Currently the West Nile Virus (WNV) is widespread throughout the U.S. This mosquito-borne virus has caused much concern in some areas. The state of Georgia had 8 reported cases of WNV in humans in 2006, while Florida had 3 cases of WNV in humans in 2006. The principal carriers of the WNV belong to the Culex genus (a genus is a group of similar species). These mosquitoes are not common along the coast of Georgia or Florida in the areas where we will be conducting the study. The percentage of mosquitoes carrying WNV is small. Of those people bitten by an infected mosquito only a small percentage will contract WNV. Only a few of those people developing symptoms of WNV, will

Page 15 of 31

Mosquito Repellent Field Test, Florida & Georgia

Protocol No.: G0590307001A044 ICR Project No.: 0307-059-0155

develop serious symptoms. Most people who have developed serious symptoms have been the elderly or those with a compromised immune system. The most common symptoms of WNV are mild illness with fever, headache, and body aches. While the risk of contracting WNV is considered to be low, no guarantees can be offered. After the study completion, any subjects experiencing any of the above symptoms should seek medical attention. In the event that a study related injury or illness should occur, test subjects would be instructed to seek medical attention through a health care provider, at ICR's expense. Test subjects would be instructed to submit study related bills to ICR. ICR will incur the cost of any study related bills.

#### BENEFITS

The purpose of this proposed insect repellent efficacy field study is to determine the protection time that can be reliably anticipated from use of these products. Field studies, such as the one proposed, have been long considered by the EPA (and the sponsor) to be the most realistic and reliable testing method available to predict protection time of a topically applied insect product. While the sponsor is an obvious beneficiary of the proposed test, the resulting information on the performance of the products will also directly benefit consumers because it will substantiate which insect pests will be repelled and provide realistic expectations for protection time. Clearly, both the study sponsor and consumers benefit from the performance of this study to provide the data required under FIFRA to substantiate this pesticide product's label claims. Specifically, FIFRA guidelines require human efficacy test data on insect repellents intended to be applied directly to the skin claiming to repel insect vectors such as mosquitoes.

Insect repellent products help prevent annoying bites and likely serve to decrease the potential spread of some diseases. It is known that consumers use insect repellents to help reduce the risk of WNV and other vector-borne diseases as stated by the CDC. The proposed study will attempt to substantiate that the test articles repel mosquitoes and will provide the user with a reliable estimate of protection time that can be anticipated under real-life conditions. It is important to bring such new products to market so that consumers can have access to alternative formulations that work best for them. That is, some formulations seem to provide longer protection times to certain individuals or simply be more convenient, pleasurable, or preferable to use (i.e., convenient product form or method of application, fragrance preferences, combination with sunscreen or skin care ingredients, aversion to or a preference for certain active ingredients, etc.).

#### TEST SUBJECTS

Eligibility requirements:

Sex:

Male/Female

Age:

18 to 65

Race:

No exclusions

Literacy:

Test subjects must be able to read, speak, and understand English

Page 16 of 31

Protocol No.: G0590307001A044 ICR Project No.: 0307-059-0155

#### Ineligibility reasons:

1. Test subjects can not participate if they are pregnant or breastfeeding.

2. Test subjects can not be a permanent full time employee of ICR Inc.

Test subjects must follow the requirements of the study as explained to them.

Test subjects must not be sensitive to mosquito bites.

5. Test subjects must have no known sensitivity to insect repellents or skin care products.

6. Test subjects must be attractive to mosquitoes, as evidenced by previous being bitten by mosquitoes.

7. Test subjects must not smoke or drink alcoholic beverages 12 hours prior to the test.

8. Test subjects must not use perfumed cosmetics, skin creams, shaving lotions, etc. after 12 AM before the test, and during the test.

 Test subjects must wear proper protective clothing during the test, such as their own blue jeans, heavy socks, long sleeve shirts, and a headnet and gloves provided by ICR.

#### Number of subjects and Rationale for Sample Size

The EPA Guideline (EPA/OPPTS Guideline \$10.3700) recommends at least six test subjects be used. Because of the cost of doing field studies, it is prudent to ensure data collected will give a good representation of the repellency of the test formulations. In a published paper the number of subjects required to achieve an estimated among-subjects standard deviation for specific times of 0.5 hours to 2.0 hours was calculated for protection times from 1 hour to 8 hours. The number of subjects required to achieve an estimated among-subjects standard deviation of 2.0 hours at a 95% confidence level for an 8 hour protection time was calculated to be between 10 and 11 subjects. This study, therefore, will use ten treated test subjects. There will be an additional two control subjects, plus two additional treated test subjects to replace anyone that either drops out or is ineligible to participate due to a positive pregnancy test or other unforseen circumstances. These additional two treated test subjects will help to ensure a minimum "n" of ten and will aid in protecting the privacy of any dropouts.

